“Clinical trials of medicinal products involving a minor or a child may be conducted only if the relevant medicinal product is intended for the treatment of paediatric diseases or if the purpose of the clinical trial is to optimise the dosing or regimen of the medicinal product accordingly for children or minors” and on other aforementioned data, a paediatric population **may** be included in this clinical study without prior full completion of clinical trials involving competent adult subjects.

As part of this clinical study, all patients will receive the investigational medicinal product BP-SCIG 20%, solution for subcutaneous administration, manufactured by BIOPHARMA PLASMA LLC subcutaneously.

The IMP BP-SCIG 20% will be administered at the frequency of once a week for 52 weeks, subcutaneously using a CRONO S-PID4 infusion pump, at the dose of 0.1–0.2 g/kg once a week (the dose over 4 weeks is 0.4–0.8 g/kg).

The dosing regimen shall be designed to achieve a minimum IgG level (at least 5–6 g/L), which will be measured monthly before each IMP infusion.

Efforts must be taken to maintain serum IgG within the reference range for the corresponding age group of patients.

Individual dose selection and adjustment may be required for each patient, depending on the pharmacokinetic response (IgG level) and clinical response. Threshold levels must be assessed in combination with the incidence of infectious episodes.

Dose adjustment of the IMP BP-SCIG 20% based on threshold IgG levels is performed by the Investigator based on the clinical presentation of each individual patient.

A loading dose of IMP may be required (at the Investigator’s decision): at least 0.2–0.5 g/kg (1.0–2.5 mL/kg) of body weight per week. This dose is distributed across several days, with a maximum daily dose of 0.1 to 0.15 g/kg.

After achieving a steady-state (minimal) level of IgG, maintenance doses are administered at repeated intervals (approximately once a week) to achieve a cumulative monthly dose of 0.4–0.8 g/kg. Each single dose must be administered to different anatomical locations.

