Since the bioavailability of SCIGs is 30 % lower than that of IVIGs, partly due to binding to the extracellular matrix and cleavage by tissue enzymes (Wang et al. 2008; Berger et al. 2013), a dose adjustment factor of 1.37 will be used to convert the IVIG dose to the SCIG dose. This is based on historical data for bioequivalence evaluation of these administration routes (Wasserman et al. 2010, 2011; Berger et al. 2011) and meets the requirements of the US Food and Drug Administration (US FDA), according to which the SCIG doses must be adjusted to ensure an equivalent AUC for total IgG compared to previous IVIG therapy. Dose calculation for patients who received IVIG prior to the start of their participation in the study (John W Sleasman et al. 2019):

The initial dose of SCIG

$$\text{IgG} = \frac{\text{Previous IVIG dose (in grams)} \times 1.37}{\text{Number of weeks between IVIG administrations}}$$

The dose adjustment factor of 1.37 will be evaluated in an interim pharmacokinetic (PK) analysis and modified as needed.

The first four IMP administrations are for training purposes, during which the investigational medicinal product BP-SCIG 20% for subcutaneous administration will be administered by a responsible member of the study team in a hospital setting and by the patient/legally authorised representative or parents after an appropriate training and in compliance with aseptic/antiseptic precautions under the supervision of responsible and trained members of the study team.

The study doctor determines the dose and rate of subcutaneous administration of the IMP for home-based use. The patient/their legally authorised representative or parents must be instructed regarding the use of the CRONO S-PID4 infusion pump, the administration technique, filling out the patient's diary, recognition of adverse reactions and measures to be taken in the event of adverse reactions.

Prior to use, the solution must be at room temperature and remain outside the refrigerator for at least 30 minutes. Turbid solutions and/or solutions with sediment must not be used.

To administer the IMP, a CRONO S-PID4 infusion pump and a dedicated single-use infusion set are used.

The IMP BP-SCIG 20% can be administered in sites with ample subcutaneous fat, such as the abdomen, the shoulder, and lateral thigh.

The IMP BP-SCIG 20% is administered subcutaneously using a CRONO S-PID4 infusion pump. Multiple lines can be used for administration into several sites simultaneously.

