3. STUDY OBJECTIVE AND TASKS

Primary objective of the study:

1. To confirm that the PK indices of the IMP BP-SCIG 20% are comparable with those of the BIOVEN product.
2. To confirm the adjustment factor for the dose of BP-SCIG 20% to ensure a steady-state area under the concentration-time curve (AUC) for the total IgG level, which is non-inferior to the values of BIOVEN, the drug of previous therapy.
3. To confirm that the threshold IgG levels (in administration of the IMP BP-SCIG 20% to patients with PID in a monthly dose of 0.4–0.8 g/kg, under a once a week regimen) are non-inferior compared to threshold IgG levels on previous therapy (in patients previously receiving human normal immunoglobulin products intravenously or another product of human normal immunoglobulin for subcutaneous administration), or those reported in the literature (in treatment-naïve patients).
4. Assessment of the efficacy, tolerability, safety, and pharmacokinetic parameters of BP-SCIG 20% in long-term use in patients with primary immunodeficiency with impaired antibody production.

Additional pharmacokinetic assessment objectives:

- To confirm the adjustment factor for the dose of BP-SCIG 20% to ensure a steady-state area under the concentration-time curve (AUC) for the total IgG level, which is non-inferior to the values of BIOVEN, the drug of previous therapy.
- To assess the variability of trough IgG levels in children and adolescents compared with adult patients.
- To determine the pharmacokinetic parameters (Cmax, AUC0-t, AUC0-∞, Tmax, t1/2, Kel, IR, Cl, AUCextrapol, Vd) for the IMP BP-SCIG 20% in 20 adult patients with PID, and compare them with the available published literature.
- To compare the results of pharmacokinetic data for patients who have not previously received human normal immunoglobulin products with published literature (descriptively).
- To compare the results of pharmacokinetic parameter study (Cmax, AUC0-t, AUC0-∞, Tmax, t1/2, Kel, IR, Cl, AUCextrapol, Vd) between the cohorts.

Safety and tolerability assessment tasks

- Conduct an interim safety assessment for the first 10 patients enrolled in the study who must be adults and must have received at least 4 IMP administrations.

Based on the results of such assessment (*interim report*), the possibility of enrolling patients younger than 18 years of age is determined;

- Assess the frequency of adverse events;
- Assess the incidence of adverse reactions to the IMP;

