 - Paediatric patients are required to undergo Visits 1 and 2 of the screening period. In the event of meeting the criterion “total serum IgG level ≥ 5 g/L – as confirmed by the results of at least two (2) measurements performed immediately prior to the subsequent administration of IVIG after signing the ICF”, the patient proceeds to treatment with the IMP BP-SCIG 20%, starting from Cycle 1. If the criterion is not met, then Visit 3 is performed.

- Adult patients are required to undergo Visits 1 and 2 of the screening period to determine whether they meet inclusion/non-inclusion criteria, and Visit 3 of the screening period to conduct a mandatory pharmacokinetic assessment of BIOVEN.
- For Cohort C, newly diagnosed (treatment-naïve) patients are required to undergo Visit 1 of the screening period; if meeting inclusion/non-inclusion criteria, the patient proceeds to treatment with the IMP BP-SCIG 20%, starting from Cycle 1.

Study phases. Treatment period.

The phase begins after the end of the screening period.

Cycles 1–13: These include on-site visits to the CTS: 4 visits in Cycle 1; all subsequent cycles: each first visit of the cycle (every 28 days \pm 3 days) and interim self-administrations of the product by patients in the home (every 7 days \pm 1 day) for 52 weeks. A total of 13 cycles that include 13 main on-site visits (1 visit to the CTS in each cycle), and 3 on-site visits for interim administration of the IMP. The period lasts 52 weeks.

Individualised dose titration is performed.

A loading dose of IMP may be required (at the Investigator's decision): at least 0.2–0.5 g/kg (1.0–2.5 mL/kg) of body weight. This dose is distributed across several days, with a maximum daily dose of 0.1 to 0.15 g/kg.

After achieving a steady-state level of IgG, maintenance doses are administered at repeated intervals (approximately once a week) to achieve a cumulative monthly dose of 0.4–0.8 g/kg. Each single dose must be administered to different anatomical locations. (see Section 6.1 of this Protocol).

Pharmacokinetic parameters of the IMP are assessed at Week 21 (see Table 4.2.2)

Cycle 1:

- Visit 4 (C1W1): **On-site visit** Week 1 – the first administration of the IMP BP-SCIG 20%;
- Interim administration 1(C1W2) on-site – Week 2, administration of the IMP;
- Interim administration 2(C1W3) on-site – Week 3, administration of the IMP;
- Interim administration 3(C1W4) on-site – Week 4, administration of the IMP.

Cycle 2:

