5.1. Inclusion Criteria

Table 5.1.1 – Inclusion criteria for CT subjects

No.	Inclusion criterion
1.	a signed informed written consent of the patient/patient's parents or legally authorised representative to take part in the study;
2.	children from 0 to 18 years of age, of both sexes; or adult patients: males and females older than 18 years;
3.	a diagnosis of primary immunodeficiency with impaired antibody production document-supported according to the ESID criteria, requiring replacement therapy with immunoglobulins;
4.	patients with a body weight of no less than 9.1 kg;
5.	patients who received replacement therapy with intravenous immunoglobulin (IVIG) products at intervals from 21 to 28 days at the dose of 0.4–0.8 g/kg, for at least 4 months prior to the start of the study and have total serum IgG levels ≥ 5 g/L*, which is confirmed by the results of no less than 2 measurements performed immediately before the scheduled IVIG administration after signing the ICF, or patients who received replacement therapy with subcutaneous immunoglobulin (SCIG) products at the dose of 0.4–0.8 g/kg per month, for at least 4 months prior to the start of the study, and have total serum IgG levels ≥ 5 g/L*, based on the results of no less than 2 measurements performed immediately before the scheduled SCIG administration after signing the ICF; or patients with a newly established diagnosis of PID who have not yet received replacement therapy with IgG products (treatment-naïve patients) and have a serum IgG level ≤ 4 g/L;
6.	absence of episodes of serious bacterial infections (bacteraemia or sepsis, bacterial meningitis, osteomyelitis/septic arthritis, bacterial pneumonia, visceral abscess) while taking the previous medicinal product and absence of episodes of hospitalisation for at least 3 months prior to inclusion in the study and during the screening period (prior to the first administration of the IMP BP-SCIG 20%);
7.	a negative pregnancy test (in female patients with childbearing potential); readiness to use reliable methods of contraception throughout the study period;
8.	patient's ability, in the Investigator's judgement, to comply with all the requirements of the study protocol.

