6. TREATMENT OF SUBJECTS

6.1. Treatment regimen

The IMP shall be administered subcutaneously.

All patients will receive the investigational medicinal product BP-SCIG 20%, solution for subcutaneous administration manufactured by BIOPHARMA PLASMA LLC.

The IMP BP-SCIG 20% shall be administered at the frequency of once a week for 52 weeks, subcutaneously using a CRONO S-PID4 infusion pump.

The dosing regimen shall be designed to achieve a trough IgG level (at least 5–6 g/L), which will be measured before the next infusion.

Efforts must be taken to maintain serum IgG within the reference range for the corresponding age group of patients.

Individual dose selection and adjustment may be required for each patient, depending on the pharmacokinetic response (IgG level) and clinical response. Threshold levels must be assessed in combination with the incidence of infectious episodes. To reduce the risk of infection, it may be necessary to increase the dose and aim to achieve higher trough IgG levels.

A loading dose of IMP may be required (at the Investigator's decision): at least 0.2–0.5 g/kg (1.0–2.5 mL/kg) of body weight. This dose is distributed across several days, with a maximum daily dose of 0.1 to 0.15 g/kg.

After achieving a steady-state (minimal) level of IgG, maintenance doses are administered at repeated intervals (approximately once a week) to achieve a cumulative monthly dose of 0.4–0.8 g/kg. Each single dose must be administered to different anatomical locations.

Since the bioavailability of SCIGs is 30 % lower than that of IVIGs, partly due to binding to the extracellular matrix and cleavage by tissue enzymes (Wang et al. 2008; Berger et al. 2013), a dose adjustment factor of 1.37 will be used to convert the IVIG dose to the SCIG dose. This is based on historical data for bioequivalence evaluation of these administration routes (Wasserman et al. 2010, 2011; Berger et al. 2011) and meets the requirements of the US Food and Drug Administration (US FDA), according to which the SCIG doses must be adjusted to ensure an equivalent AUC for total IgG compared to previous IVIG therapy. Dose calculation for patients who received IVIG prior to the start of their participation in the study (John W Sleasman et al. 2019):

The initial dose of SCIG

$$\text{IgG} = \frac{\text{Previous IVIG dose (in grams)} \times 1.37}{\text{Number of weeks between IVIG administrations}}$$

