The recommended infusion rate must be followed strictly. During the initial administration, the patients shall remain under supervision for the entire duration of the infusion period to detect hypersensitivity to the active ingredient or to any of the excipients. Monitoring for any adverse symptoms shall be in place. It is forbidden to administer the IMP BP-SCIG 20% in pronounced thrombocytopenia or other disorders of haemostasis.

Potential complications described in this Protocol (see Section 2, item 3) can usually be avoided in adherence to:

- slow start of administration, from the infusion rate of 10 mL/kg/line;
- careful monitoring of patients' well-being in relation to any symptoms throughout the infusion period. In particular, patients who have not previously received human normal immunoglobulin, patients who have switched from an alternative immunoglobulin product, or if a long period of time has passed since the previous administration shall be monitored by health care workers during the first infusion and throughout the first hour afterwards to identify any potential adverse manifestations.

In all other cases, the patient's well-being must be monitored for at least 20 minutes after the administration.

In case of an adverse reaction, either the infusion rate must be reduced, or administration must be stopped. If an AE develops, the necessary treatment will depend on the nature and the severity of the AE.

The route of administration and dosing shall not exceed the maximum single and course doses that can be used in patient treatment, within the limits specified in "*Guideline on core SmPC for human normal immunoglobulin for subcutaneous and intramuscular administration*" EMA/CHMP/BPWP/143744/2011 rev.1 26 February 2015, and "*Guideline on the clinical investigation of human normal immunoglobulin for subcutaneous and/or intramuscular administration (SCIg/IMIg)*" EMA/CHMP/BPWP/410415/2011 rev.1 23 July 2015.

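### The stated IMP dose range of 0.4–0.8 g/kg per 4 weeks conflicts with the 1.37 IVIG conversion, which gives up to 1.096 g/kg from the admitted doses, and the protocol does not say which governs

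*Protocol*

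**What the plan says.** **Range.** Section 2.4 states that all patients receive the IMP, once a week for 52 weeks, "at the dose of 0.1–0.2 g/kg once a week (the dose over 4 weeks is 0.4–0.8 g/kg"). Sections 2.4, 4.2 and 6.1 give the same range for maintenance after steady state, with weekly doses "to achieve a cumulative monthly dose of 0.4–0.8 g/kg". Primary objective 3 in Section 3 concerns trough IgG "in a monthly dose of 0.4–0.8 g/kg, under a once a week regimen".

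**Conversion.** Section 2.4 also says that "a dose adjustment factor of 1.37 will be used to convert the IVIG dose to the SCIG dose". Section 6.1 repeats this under "Dose calculation for patients who received IVIG prior to the start of their participation in the study": initial SCIG dose = previous IVIG dose in grams × 1.37 / number of weeks between IVIG administrations. Primary objective 2 is "To confirm the adjustment factor for the dose of BP-SCIG 20% to ensure a steady-state area under the concentration-time curve (AUC") for total IgG that is non-inferior to BIOVEN.

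**Entry.** Inclusion criterion 5 in Section 5.1 admits patients on "intravenous immunoglobulin (IVIG) products at intervals from 21 to 28 days at the dose of 0.4–0.8 g/kg". For SCIG patients the criterion says the dose is per month; for IVIG patients it does not say whether the dose is per infusion or per month.

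**Flexibility and ceiling.** Sections 2.4 and 6.1 allow individual adjustment by IgG level and clinical response, and a loading dose at the Investigator's decision. Section 6.1 adds that "The route of administration and dosing shall not exceed the maximum single and course doses that can be used in patient treatment", within limits in two cited guidelines, and gives no figure.

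**The concern.** For part of the admitted IVIG population the range and the formula give different doses. The sentence in Section 2.4 covers the whole 52 weeks, so the conflict exists from the first dose. It continues into maintenance, because nothing says whether a converted dose above the range stays, is reduced, or when.

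Three things follow for the analysis:

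- **Objective 2 and objective 3 assume different doses.** Objective 2 relies on the converted dose; objective 3 is stated for 0.4–0.8 g/kg per month. Above the crossover one patient cannot satisfy both.
- **The Week 21 AUC may not test the factor.** IMP pharmacokinetics are assessed after about 4 months, when the maintenance range would apply. If it is applied, the AUC comparison in Section 9.6 compares BIOVEN with a dose ratio below 1.37.
- **Per-protocol status is unclear.** Section 9.1 limits the main efficacy analysis to patients who received full protocol therapy without significant deviations, and Section 11.2 classes therapy inconsistent with the protocol as a substantial deviation. A dose from the formula but outside the range meets one protocol statement and breaches another.

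Sites could resolve this differently, and Section 9.2 plans only 8–10 adults per cohort.

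**Working it through.** **Inputs.** IMP range 0.1–0.2 g/kg weekly (Section 2.4); factor 1.37 and formula (Sections 2.4 and 6.1); prior IVIG dose 0.4–0.8 g/kg every 21–28 days (Section 5.1).

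**1. The stated range is consistent in itself.** 4 × 0.1 = 0.4 and 4 × 0.2 = 0.8 g/kg per 4 weeks.

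**2. Conversion at a 28-day interval.**
- Lower end: 0.4 × 1.37 / 4 = 0.137 g/kg weekly; × 4 = 0.548 per 4 weeks.
- Upper end: 0.8 × 1.37 / 4 = 0.274 g/kg weekly; × 4 = 1.096 per 4 weeks.
- Against the stated top: 1.096 / 0.8 = 1.37, that is 37% above.

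**3. Conversion at a 21-day interval, under the two readings of criterion 5.**
- Dose per 4 weeks: 0.8 × 3/4 = 0.6 g/kg per infusion; 0.6 × 1.37 / 3 = 0.274 weekly, again 1.096 per 4 weeks.
- Dose per infusion: 0.8 × 1.37 / 3 = 0.365 weekly, or 1.461 per 4 weeks.

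**4. Prior dose at which the range is passed.**
- 28-day interval, or per-4-week reading at any interval: 0.8 / 1.37 = 0.584 g/kg per 4 weeks.
- 21-day interval, per-infusion reading: 0.8 × (3/4) / 1.37 = 0.438 g/kg per infusion.

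The first threshold lies just below the midpoint, 0.6, of the admitted range; a prior dose of 0.6 every 28 days already converts to 0.6 × 1.37 = 0.822.

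**5. Share of the converted dose received if the patient is held to 0.8 per 4 weeks (28-day interval).**

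| Prior IVIG dose (g/kg) | Converted, per 4 weeks | 0.8 / converted |
|---|---|---|
| 0.6 | 0.822 | 97% |
| 0.7 | 0.959 | 83% |
| 0.8 | 1.096 | 73% |

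At a prior dose of 0.8 the effective factor is at most 0.8 / 0.8 = 1.00.

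**6. Illustrative effect on AUC at a prior dose of 0.8.** Assume that 1.37 is correct, that exposure is proportional to dose, that both AUCs are on the same time basis, and that a fraction e of the BIOVEN AUC is endogenous IgG. The protocol gives no value for e. The expected IMP/BIOVEN ratio is e + (1 − e) × 0.730:
- e = 0: 0.730
- e = 0.2: 0.2 + 0.8 × 0.730 = 0.784
- e = 0.4: 0.4 + 0.6 × 0.730 = 0.838

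**The case against.** The best defence is that Section 6.1 is staged: the formula sets the initial dose and 0.4–0.8 g/kg is the maintenance range after steady state, so a start above a later range is not in itself contradictory. The range also does not read as a hard cap, since a loading dose may exceed it and Section 6.1 allows increases to reach higher troughs. The ceiling may lie in the cited guidelines, which cannot be checked here. Because titration is allowed, the Week 21 dose may depart from 1.37 in any patient, and the protocol expects to confirm or recalculate the factor. A dose from the protocol's own formula is arguably protocol-specified therapy. Finally, the primary infection-rate test does not use the conversion, and patients from Cohorts A and C are unaffected.

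Much of this narrows the point without removing it. The staged reading leaves the 52-week sentence in Section 2.4, which covers the starting dose, and it sharpens the AUC problem: at Week 21 the maintenance range would have displaced the factor under test. The loading dose is a separate provision, and the adjustment clauses do not say whether doses may leave the range. The guideline reference states no figure and does not mention the conversion. That titration can move doses anyway is true, and is a further reason to analyse the dose ratio actually given. The per-protocol argument is reasonable for a site that follows the formula, but the protocol should say so. The limits on scope stand: only prior-IVIG patients above the threshold are affected, and the AUC ratios are illustrations at the top of the admitted range.

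**Conclusion.** The contradiction is real. The protocol's own formula, applied to its own entry criterion, gives up to 1.096 g/kg per 4 weeks against a stated 0.4–0.8, and exceeds the range for prior doses above 0.584 g/kg every 28 days. The figures 1.461 and 0.438 hold only if the admitted IVIG dose is read as per infusion every 21 days. These are limits on the admitted range: the protocol gives no distribution of prior doses, so the number of patients affected cannot be stated.

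The effect on primary objective 2 is conditional. If the range is applied, a patient at the top of the entry range gets 73% of the converted dose, with an expected AUC ratio of 0.73 to 0.84 under the assumptions above. If the formula is applied, the AUC comparison is sound on this point, but the dose is outside the range and its per-protocol status is open. The primary infection-rate hypothesis is not changed by the conversion itself; it is touched only through who counts as per protocol. Because the starting dose of eligible patients has two protocol answers and a primary objective depends on which is followed, this must be corrected.

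**What to change.** - Reconcile Sections 2.4, 3, 4.2, 5.1 and 6.1 so that each eligible prior-IVIG patient has one protocol-defined rule for the starting and the maintenance dose. State which statement prevails where the converted dose and the range differ. The choice of dose belongs to the sponsor and its clinicians.
- State in inclusion criterion 5 whether the IVIG dose is per infusion or per 4 weeks.
- State in Section 9.1 that a dose following the reconciled rule is not a protocol deviation for the analysis sets.
- Add a sentence to Section 9.6 that the AUC comparison and the adjustment-factor analysis use the ratio of doses actually given.

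The cost is protocol wording, with a substantial amendment if the range or the entry criterion moves. No new data are needed: prior dose and schedule are already entered in the eCRF (Section 4.9), and each home dose is recorded in the diary and transferred (Sections 4.9 and 6.3.2).
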